3.5.2. Withdrawal of Participants

Participants may withdraw from study participation at any time. The Observer will attempt to acquire all study related information and document the reason for withdrawal. Information and data collected up to the time of participant's withdrawal from the study may be used without identifying any personal information, consistent with the informed consent signed for enrollment, unless the participant provides a written request to limit the use and sharing of their study data.

Investigator(s) may separately determine if participation by any subject in this study should be limited or be withdrawn. The investigator may close the study prematurely for any reasons including administrative decisions.

CONFIDENTIAL Page 14 of 45

4. STUDY PROCEDURES

4.1 Recruitment

Participants will be recruited from up to seven (7) geographically distinct Canadian sites. Prospective participants will be representative of the Canadian HIV testing population, including a minimum of 400 participants at risk for HIV infection (e.g. IDU, MSM, etc.).

Version 1: 13-Jul-2021

Recruitment of participants will be done through i) clinic and community-based recruitment - after strategic planning and relevant research, the co-investigators will identify active HIV testing clinics and institutions that have an appropriate participant base, ii) word-of-mouth recruitment - participants will be encouraged to tell others about the study and iii) various media channels.

Once participants have been identified through recruitment, they will be approached, informed about the study and the role they will play in the study procedure. These participants must consent to be tested for HIV as per the study site's standard of care procedures before enrolling in the study. These sites will direct all investigative and administrative functions for the study. The participating sites must have the ability to comply with all local government requirements for HIV testing and reporting.

It is anticipated that the target population for this study will include a mix of highrisk and low-risk populations. The total study population will include a minimum of 900 participants whose HIV status is unknown. All 900 participants will be assessed for usability and label comprehension and 400 from the 900 participants enrolled will be asked to participate in a results interpretation study using premade devices that will mimic the different test results that might be observed.

Study numbers for each of the study objectives were not computed. They were determined to meet compliance requirements from the Health Canada Guidance Document: Guidance for Manufacturers pf Human Immunodeficiency Virus (HIV) Rapid Diagnostic Tests (RDTs) for use at the point of Care of for Self-Testing.¹⁴

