2. STUDY OBJECTIVES

The primary objectives of this study will be to:

- 1) Evaluate the device performance, i.e. sensitivity and specificity, compared to laboratory reference testing
- 2) To document if intended users (non-professional "lay users"), can successfully perform the steps to use the OraQuick® HIV Self-Test, without product familiarization or demonstration (accuracy/usability)
- 3) To document if intended users, (non-professional "lay users"), can successfully interpret contrived strong positive, weak positive, negative, and a range of invalid results (test results interpretation) and
- 4) To document if intended users can understand the key messages in the labeling (label comprehension).

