3. STUDY DESIGN

3.1. Overall Study Design

[figure not shown]
This is a cross-sectional study that employs both observational and interview-based methods.

A minimum of 900 lay participants (non-healthcare professional and inexperienced in HIV self-testing) will read the instructions for use (IFU) and conduct the OraQuick® HIV Self-Test. They will not be provided any training prior to use of the test. A trained healthcare provider or researcher (trained Observer) will watch, and document use of the test and independently read the participants self-test result. The participants will then complete a questionnaire to share their opinion on usability and label comprehension of this test. A minimum of 400 participants will also be provided five mock devices with different results and asked to interpret those results i.e. strong positive; weak positive, negative, invalid with no control and no test line, and invalid with no control and a positive test line.¹⁴

All participants will also have a venous blood sample collected for testing of plasma at a central laboratory with a 4th generation HIV enzyme immunoassay (EIA) that will serve as the Comparator Method (CM). All self-tests will be confirmed using a Canadian standard HIV testing algorithm. The sensitivity and specificity of the self-test result will be calculated relative to the "clinical truth" of the participants' HIV status determined by the confirmatory test process, where applicable. Participants will be instructed to return to the clinic for a follow-up visit, two (2) weeks after self-testing to obtain their laboratory test results which will be their official result.

CONFIDENTIAL Page 10 of 45

Flowchart representation of the overall process from recruitment through Confirmatory testing:

CONFIDENTIAL Page 11 of 45

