3.5. Selection and Withdrawal of Participants

3.5.1. Inclusion/Exclusion Criteria

Participant's eligibility to enroll will be based upon inclusion and exclusion criteria and the signing of informed consent. The requirements for inclusion/exclusion are as follows:

Inclusion Criteria

Participants considered eligible for inclusion are those who:

- 1. Are 18 years of age and older
- 2. Are able to speak / read / write English or French
- 3. Have presented for voluntary testing for HIV infection in the clinic or community based setting
- 4. Are willing to participate in the study site's standard of care HIV counselling and testing program and receive the study site's standard of care test results
- 5. Are willing to be a participant in the study
- 6. Are able to provide informed consent i.e. understands and signs the informed consent form

CONFIDENTIAL Page 13 of 45

- 7. Are able to complete the required testing on the allocated testing day
- 8. Are willing to provide the necessary oral fluid and venipuncture blood for use in the study protocol testing methods.

Version 1: 13-Jul-2021

9. Are of unknown HIV status (last HIV negative test must be a minimum of 3 months prior)

Exclusion Criteria

Participants considered ineligible for participation in the study are those who meet any of the following exclusion criteria:

- 1. Do not meet all the inclusion criteria
- 2. Are known HIV positive
- 3. Are on antiretroviral therapy (ART) or anti-HIV medications for the treatment of HIV, either as pre-exposure prophylaxis (PrEP), post-exposure prophylaxis (PEP) or experimental vaccine
- 4. Have any experience or have ever conducted a rapid diagnostic self-test for HIV or any other infectious disease
- 5. Are currently participating in a concurrent trial of HIV self-tests
- 6. Are investigator site employees or immediate family members of sponsor or investigator site employee
- 7. Are a practicing medical healthcare professional (doctor, nurse or HIV counsellor that performs HIV testing with Rapid Tests)
- 8. Any condition which, in the opinion of the Observer, would make the participant unsuitable or unsafe for enrolment or could interfere with the completion of the assessment and questionnaire etc. or bias the outcome, e.g. being unable to see / read by forgetting to bring reading glasses, being intoxicated, acute sickness, visibly distressed.

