4.11 Interpretation of Results – Mock Devices

At the end of the self-testing process, the Observer may ask subjects to participate in a 'Mock Result Interpretation' study that will involve interpreting a separate set of OraQuick® HIV Self-Test results prepared by the manufacturer. Participation is voluntary and up to 400 participants recruited from the 900 participants who consented for the device accuracy study will conduct this Mock Result Interpretation. If participant agrees to participate, they will be presented with five (5) OraQuick® HIV Self-Test mock result types and asked to interpret the results using the Self-Test instructions for use (IFU) as a guide. The five (5) mock devices will be the following:

Version 1: 13-Jul-2021

- 1. Strong Positive
- 2. Weak Positive
- 3. Negative
- 4. Invalid (no control line present, test line present)
- 5. Invalid (no control line or test line present)

Mock devices will be presented in a randomized order to control bias.

Although the self-test study participants will be interpreting the results of their own OraQuick® HIV Self-Test, the purpose of this sub-study is to document if intended users, (non-professional and inexperienced in HIV self-testing), can successfully interpret contrived/mock strong positive, weak positive, negative and invalid results. Results of this interpretation will be recorded by the Observer on Appendix G - Participant's Mock OraQuick® HIV Self-Test Result Interpretation Record Form.

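### Word-of-mouth recruitment carries no stated request not to disclose the test and no listed item on prior briefing, so second-hand familiarization of later participants can be neither prevented nor checked

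*Combined protocol and SAP*

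**What the plan says.** Section 4.1 lists three recruitment routes: clinics and community settings, word of mouth, and media. On the second it says "participants will be encouraged to tell others about the study". It gives no expected share for any route and does not say what participants may or may not pass on.

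Primary objective 2 (section 2) asks whether lay users "can successfully perform the steps to use the OraQuick® HIV Self-Test, without product familiarization or demonstration (accuracy/usability". Objective 3 asks whether they "can successfully interpret contrived strong positive, weak positive, negative, and a range of invalid results". Objective 4 concerns understanding of the key messages in the labeling. The wording about familiarization appears in objective 2 only, although sections 3.1 and 4.11 also describe the participants as inexperienced in HIV self-testing.

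Four provisions protect the naive-user condition in part:

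- Section 3.1: "They will not be provided any training prior to use of the test".
- Section 3.5.1, exclusion 4: "Have any experience or have ever conducted a rapid diagnostic self-test for HIV or any other infectious disease".
- Section 3.5.1, exclusion 8: "Any condition which, in the opinion of the Observer, would make the participant unsuitable or unsafe for enrolment". It extends to conditions that could bias the outcome.
- Section 4.11: "Mock devices will be presented in a randomized order to control bias".

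The data items in sections 4.3 to 4.5 include experience with HIV testing. They do not include how the person heard of the study or whether an earlier participant explained the test. Section 6.4 lists no subgroup by recruitment route.

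**The concern.** Someone who has finished the visit has read the instructions, used the kit and answered the comprehension questions, and may also have read the five mock devices. If that person describes the procedure to a friend who then enrols, the friend is no longer the unprepared first-time user whom objective 2 is meant to describe. The label-comprehension items in section 4.12 are also easy to pass on, for example what to do after each result and how long to wait after food or drink.

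The practical difficulty is that nothing listed would show whether this had happened. If a regulator asked whether the 900 users were truly naive, the recorded items could not answer, and referral history cannot be recovered reliably after enrolment. A bias of this kind also does not shrink as the sample grows.

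**Working it through.** **No figure of the plan to reproduce.** Section 4.1 says the study numbers were not computed, and section 6.7 takes them from regulatory guidance. There is no expected success rate, margin or threshold for usability.

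**Step 1: do the existing provisions reach briefing by an earlier participant?**

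- The no-training statement limits what the study provides. It does not govern what a participant hears elsewhere.
- Exclusion 4 concerns a person's experience of, or conduct of, a rapid self-test. Being told how one works is not clearly covered.
- Exclusion 8 could be stretched to cover it, but its examples are missing reading glasses, intoxication, sickness and distress.
- Random order of the mock devices makes a remembered sequence useless. The set of five result types remains fixed, and the provision does not touch usability or comprehension.

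None of the four clearly covers second-hand familiarization.

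**Step 2: size of a possible bias.** Let f be the share of participants briefed by an earlier participant, p0 the success rate of naive users and p1 that of briefed users.

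- Observed success = (1 − f) × p0 + f × p1
- Bias = f × (p1 − p0)

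The documents give none of the three, so all values below are assumptions. Because p1 cannot exceed 100%, the upward bias cannot exceed f × (100 − p0) points.

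| p0 | ceiling at f = 10% | f = 20% | f = 30% |
|---|---|---|---|
| 80% | 0.10 × 20 = 2.0 | 0.20 × 20 = 4.0 | 0.30 × 20 = 6.0 |
| 90% | 0.10 × 10 = 1.0 | 0.20 × 10 = 2.0 | 0.30 × 10 = 3.0 |
| 95% | 0.10 × 5 = 0.5 | 0.20 × 5 = 1.0 | 0.30 × 5 = 1.5 |

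If briefing only halves the failure rate, each entry halves. If it does not help, each entry is 0.

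**Step 3: compare with sampling error.** Section 4.1 gives n = 900 for usability and label comprehension. Sections 3.1 and 6.7 give a minimum of 400 for mock reading. Section 6.3 specifies Wilson intervals for sensitivity and specificity only; I use the same method here as a yardstick.

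Half-width = z × √[p(1 − p)/n + z²/(4n²)] / (1 + z²/n), with z = 1.96.

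| p | n = 900 | n = 400 |
|---|---|---|
| 80% | 2.61 points | 3.91 points |
| 90% | 1.96 points | 2.95 points |
| 95% | 1.43 points | 2.17 points |

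**Step 4: when would the ceiling equal the half-width at n = 900?** Divide the half-width by (100 − p0):

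- p0 = 80%: 2.61 / 20 = 13%
- p0 = 90%: 1.96 / 10 = 20%
- p0 = 95%: 1.43 / 5 = 29%

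The possible bias therefore runs from nil to more than the sampling error. The documents do not allow a point in that range to be chosen.

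**The case against.** The case on the other side is substantial.

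- **The phrase in section 4.1 is ordinary recruitment wording.** It does not invite anyone to describe steps or answers, and it does not say when the encouragement is given. This stands. The point is the absence of a stated limit, not an instruction to disclose.
- **Objective 2 can be read as excluding only familiarization given by the study.** Read with the no-training statement, this is reasonable. However, the purpose is to describe unprepared lay users, and briefing from a peer weakens that description just as briefing from staff would.
- **Part of the documents cannot be seen.** The consent template is not in the supplied text and the forms appear as titles only. Section 4.3 introduces what the questionnaire captures with examples rather than a closed list. A non-disclosure request or a referral question may already exist. This stands, and the point is confined to the supplied text.
- **Mock reading is less exposed.** It follows the participant's own test, is done with the instructions in hand and in random order, and involves only about 400 of the 900. This stands.
- **No stated decision depends on it.** Section 6.6 reports usability as a percentage without a success threshold. This stands and limits the importance.

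A reader might go further and infer that usability and mock-reading success are inflated. The documents do not show that: they give neither the share recruited by word of mouth nor any effect of briefing, and inaccurate hearsay could lower success. A reader might also multiply a 30% share by a 15-point gain to reach 4.5 points. From a naive rate of 90% that gain is impossible, because the ceiling is 0.30 × 10 = 3.0 points. Treating every referred participant as briefed would also overstate the share.

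**Conclusion.** The point holds as a gap in prevention and in checking. The plan promotes a route by which later participants could become familiar with the product, and the supplied text neither asks for non-disclosure nor lists an item that would reveal briefing. The gap bears mainly on objective 2, and more weakly on label comprehension and mock reading.

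No bias is demonstrated. An upward direction is plausible and the size is unknown. The 2-point and 3-point ceilings rest on an assumed naive success of 90%, briefed shares of 20% and 30%, and briefed users who never fail. No effect on sensitivity or specificity is claimed. This is a cheap improvement to make before enrolment, not a defect that invalidates the study.

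**What to change.** Keep the word-of-mouth route and make three changes.

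1. **Section 4.1 and visit close-out.** State that participants may pass on the study's existence and contact details, and are asked not to describe the kit steps, results, mock devices or questions.
2. **Enrolment questionnaire (section 4.3, Appendix C).** Add two items if they are not already there: heard of the study from a past participant (yes/no), and told how the test works (yes/no).
3. **Section 6.4.** Repeat the usability and label-comprehension estimates without those who were told how the test works, with mock reading as supportive. Report how many answered yes to each item.

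The cost is one sentence at close-out, two tablet questions and one extra table. No sample size or visit changes. The second item relies on self-report, so it would reduce the uncertainty rather than remove it.

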4.2 Informed Consent

Informed Consent will be obtained from individuals before they are allowed to participate in the trial. The Informed Consent form will be reviewed and approved by a Research Ethics Board (REB) or Ethics Committee (EC). The principal investigator or his/her designated staff will provide the Informed Consent for participation in this study to the participant, explain the nature of the study and sample collection procedures, and answer any questions that might arise. The Informed Consent will contain general information about the study (see Appendix B).

CONFIDENTIAL Page 15 of 45

Participants will be consented prior to conducting any study-related procedures. Participants will be encouraged to ask questions to ensure the entire process is clearly understood. Study participants will be instructed that they may reject the specimen collection procedure and withdraw from the study at any time. Participants must agree to and submit their Informed Consent form prior to formal enrolment into the study. The informed consent will be offered after verbal explanation of the study procedures in English/French. The Informed Consent will have the appropriate signature lines that need to be filled out to complete the Informed Consent process, facilitating enrollment.

4.3 Enrollment Questionnaire - Review Eligibility Criteria

Participants providing informed consent and meeting inclusion criteria may be eligible to participate in the study. Participants will be administered an Enrolment Questionnaire to ascertain successful qualification for enrolment (Appendix C). The questionnaire clearly outlines the inclusion and exclusion criteria. If participants satisfy all the inclusion criteria and none of the exclusion criteria, eligibility for enrolment can be confirmed. All participants evaluated for participation in this study will be assigned a unique participant identification number (PID number). Enrolment questionnaires will capture information such as PID Number, Age, Nationality and Employment status. Participants that do not satisfy inclusion/exclusion criteria are documented and reported as exclusions. In addition, the reason for the enrolment failure will also be recorded.

The PID number will also be considered the Participant Number, following the format below:

- AA = Study name
- BB = Province of Investigational Site; example ON for Ontario, QC for Quebec.
- CC = Investigational site number identifier
- DDD = Sequential sample identifier, starting at 001 for all participants For example, Self-Test-Ontario-Site#1-Participant#1: ST-ON-01-001:

Multiple copies of pre-printed labels with the PID Number will be provided to the study site facility. These labels will be placed on the forms and whole blood samples.

The enrollment questionnaire will gather the following demographic information:

- Age
- Ethnicity
- Gender
- Experience with HIV testing
- HIV Status/Risk
- Language capabilities
- Visual Status (glasses/contacts)

CONFIDENTIAL Page 16 of 45

4.4 Background Data

For all study participants meeting inclusion/exclusion criteria, background data to be collected will include:

Version 1: 13-Jul-2021

- Experience with HIV testing
- Date of last HIV test (approx.)
- Highest education level achieved (None, Primary, Secondary / High School, College/University or Higher)
- Language capabilities
- Employment status (employed/unemployed)
- Visual status (use of reading glasses)
- Reading/writing impairment

4.5 Medical History/ Oral Health

For all study participants meeting inclusion / exclusion criteria, their self-reported medical history will be obtained and documented. In addition to any self-reported medical conditions, specific medical conditions will be queried, in particular the study participant's HIV status. Data to be documented will include:

Medical History - Participants may choose to report their medical history; this will be documented and archived for statistical review. Information may include:

- Self-reported HIV status.
 - o Unknown, never tested
 - Unknown, previously tested negative at least three (3) months prior. The date and location of testing along with the type of test is to be recorded, if known.
 - HIV positive. (If yes, the exclusion criterion will be applied)
- Self-reported medical conditions (e.g. diabetes, hypertension, sexually transmitted infections, etc.).
 - Self-reported Ocular health / visual impairment
 - Requirement for, and current use of, glasses or contacts
 - Any condition that specifically affects vision (besides the need of glasses or contacts, (e.g. macular degeneration, etc.)
 - Any other medical condition that the participant has experienced or currently reports, and the date of diagnosis.
 Study participants' self-report will serve as the source of these data and verification in medical records is not required.
- Self-reported risk category:
 - Unprotected sex with men
 - Unprotected sex with women
 - Multiple sexual partners
 - Injection drug user

CONFIDENTIAL Page 17 of 45

- o Born to an HIV positive mother
- Sexual partner is HIV positive
- Sexual partner is a bisexual male
- Other
- Self-reported pregnancy, if applicable.

Oral Health

 Responses to specific oral health questions - Specific presence or absence of oral health conditions

Version 1: 13-Jul-2021

- Cavities and/or fillings
- o Braces
- Periodontal disease and/or bleeding gums
- Oral fixtures; full or partial dentures
- Specific last use of oral products, food and drink
 - Last food and/or beverage consumption
 - Tooth paste
 - Mouthwash or oral rinse
 - Smoking or smokeless tobacco

4.6 Concomitant Medications

For all study participants meeting inclusion / exclusion criteria, their self-reported current concomitant medications will be obtained and documented. Data documented throughout the study will include:

- General concomitant medications, and herbal or dietary supplements.
- Any medication to treat or prevent HIV (ARV and/or PrEP).

